## **12.2 Lesional and Non-Lesional Skin Assessments**

Non-invasive patch-based skin sampling will be taken from psoriasis lesion and non-lesional (perilesional) skin, chosen at the discretion of the investigator at Baseline to be representative of the subject's overall plaque psoriasis, and sent to DermTech (La Jolla, CA) for RNA isolation and transcriptomic analysis by a blinded independent evaluator.

Please refer to the DermTech Manual for specifics regarding the harvesting and handling of these samples.

## **12.3 Blood Biomarker Analysis**

Plasma samples will be collected, stored at -70°C, and sent under frozen conditions to Charles River Laboratories for cytokine assays and RASP ELISAs for malondialdehyde and 4-hydroxynonenal (Senneville, Quebec, Canada).

At Visit 4 only, a plasma sample (taken from subjects between 2 and 4 hours after test article dosing) will also be sent to Charles River Laboratories (Mattawan, MI) for drug metabolite analysis. Note: the laboratory designated to perform these services is subject to change based on availability or other factors.

Further details will be provided in a laboratory manual.

## **12.4 Urine Drug Metabolite Analysis**

At Visit 4 only, urine samples will be taken from subjects between 2 and 4 hours after test article dosing and sent to Charles River Laboratories (Mattawan, MI) for urine drug metabolite analysis.

Further details will be provided in a laboratory manual.

## **12.5 Urine Pregnancy Tests**

The UPTs will be performed at the trial site as permitted by applicable local and national health authority laws and regulations. In the United States, the site must be registered and conform to CLIA regulations for such testing (possesses a current valid CLIA Certificate

of Waiver or higher), or at an appropriately registered reference laboratory. The investigator will report the UPT results on the eCRFs, in the subject's medical records, and in independent records maintained at the trial site. The UPT used must have a minimum sensitivity of 25 mIU of β-hCG/mL.

### **13. END OF TRIAL CRITERIA**

At the end of each subject's participation in the trial, the investigator will complete an End of Study Disposition form for all completed and discontinued subjects.

#### **13.1 Completion of the Trial**

Subjects who complete the 12-week course of treatment and Visit 6/EOT procedures as specified in the protocol will be considered to have completed the trial.

#### **13.2 Subject Discontinuation**

A subject may be withdrawn from the trial prior to completion for any of the following reasons:

- AEs
- Death
- Lack of efficacy
- Lost to follow-up
- Non-compliance with study drug
- Physician decision
- Pregnancy
- Progressive disease
- Protocol deviation
- Study terminated by Sponsor
- Withdrawal by subject; NOTE: if the subject decides to withdraw from the trial due to an AE then it should be classified as withdrawal due to an AE
- Other (e.g., any reason that may affect the outcome of the trial or safety of subjects)

If a subject withdraws from the trial prematurely for any reason, the site should make every effort to have the subject return to the clinic to perform all of the required visit activities and to collect and reconcile all test articles (if applicable). If the subject will not return to the clinic, the site should make every attempt to contact the subject; otherwise the subject will be considered lost to follow-up.

---

 Defined as the lack of expected or desired effect related to a therapy.

 Defined as a disease process that is increasing in extent or severity.

When a subject is withdrawn from the trial for a test article related AE (as defined in Section 14.2), when possible, the subject should be followed until resolution or stabilization of the AE. If the subject is discontinued from the trial due to pregnancy, the pregnancy and its outcome should be followed.

Subjects who are prematurely withdrawn or discontinued from the trial will not be replaced.

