### **5.1.3 Subject Withdrawal Criteria**

Procedures for handling subjects who are discontinued from the trial are described in Section 13.2. Subjects who are discontinued will not be replaced.

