### 14.3 Subject Stopping Rules

Safety and tolerability data will be reviewed on an ongoing basis by the Medical Monitor and stopping rules will be applicable starting with dosing of the first subject.

Subjects will be discontinued from dosing, but will continue to be followed in the trial, if any of the following occurs:

- $\geq$  Grade 3 (Common Terminology Criteria for Adverse Events [CTCAE] v5.0) AE or clinically significant laboratory abnormality OR  $\geq$  Grade 2 (CTCAE v5.0) AE (or Grade 3 if a qualified subject is enrolled at Baseline with Grade 2 findings) for the system organ classes (SOCs) of cardiac disorders and/or blood and lymphatic disorders, considered related to trial drug. Any clinically significant laboratory or ECG abnormalities that may trigger a subject stopping rule must be repeated promptly to ensure accuracy and confirm the event meets stopping rule requirements.
- Severe anaphylactic reaction, including bronchospasm;

- Moderate to severe renal impairment, defined as an eGFR  $\leq 50$  mL/min/1.73m^2;  
**Note:** Dosing will be suspended until eGFR exceeds 50 mL/min/1.73m^2 for at least 2 consecutive measurements within 24 hours, at which time dosing may be resumed. A subject with out-of-range value(s) may be re-tested once before dosing is discontinued. Re-testing must occur promptly of an abnormal laboratory value(s).
- Requirement for hemodialysis; and/or
- Significant hepatic impairment, defined as an ALT or AST level  $> 3$  times the upper limit of normal (ULN) or a total bilirubin  $> 2$  times the ULN for more than 24 hours, confirmed on re-testing.  
**Note:** A subject with out-of-range value(s) may be re-tested once before dosing is discontinued. Re-testing must occur promptly of an abnormal laboratory value(s).  
Subjects will be monitored until the AEs resolve or stabilize.

In the event that any of the following are encountered, the Medical Monitor will determine if the trial must stop enrollment:

- SAE considered related to trial drug;
- $\geq$  Grade 3 (CTCAE v5.0) reaction considered related to trial drug;
- $\geq 2$  subjects are discontinued from treatment for safety reasons pertaining to trial drug; and/or
- $\geq 2$  subjects experience similar SAEs or Grade 3 (CTCAE v5.0) AEs related to trial drug.

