## 17. STATISTICAL CONSIDERATIONS

### 17.1 Sample Size

Sample size calculations were not performed, as this is primarily a safety and tolerability trial. The number of subjects (N=10) to be enrolled is standard for trials of this type.

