##### **8.7.2.2      Handling of Dropouts or Missing Data**

Missing data will not be imputed. All analyses will be based on observed data. For all by-visit analyses of clinical endpoints, the final visit is either Week 12/Visit 6 if a subject completed the study, or the discontinuation visit.

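### Protocol 13.2 permits exit from the trial, not only from test article, for lack of efficacy or progression, so a treatment failure who leaves before Day 70 has no true Week 12 measurement

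*Protocol*

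**What the plan says.** **Leaving the trial.** Protocol 13.2 opens its list with "A subject may be withdrawn from the trial prior to completion for any of the following reasons". Among the reasons are lack of efficacy, progressive disease, non-compliance with study drug, protocol deviation, AEs and physician decision. A footnote explains lack of efficacy as "Defined as the lack of expected or desired effect related to a therapy" and another explains progressive disease as "Defined as a disease process that is increasing in extent or severity". Neither gives a threshold or an earliest time. For a premature withdrawal of any kind, the site is asked to try to bring the subject back for the required visit assessments.

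**Stopping drug only.** Protocol 14.3, for its listed safety triggers, takes a different route: "Subjects will be discontinued from dosing, but will continue to be followed in the trial". Protocol 14.6 lets the Medical Monitor retain a pregnant subject for safety follow-up. No similar provision covers the efficacy, compliance or deviation reasons in 13.2.

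**Consequences for the data.** Protocol 5.1.3: "Subjects who are discontinued will not be replaced". SAP 8.7.2.2: "Missing data will not be imputed. All analyses will be based on observed data". SAP 8.7.2.1 and Table 8.5-1 place an early termination visit by study day: Days 2-41 are Week 4, Days 42-69 are Week 8, and Day 70 onward is Week 12. If a nominal visit falls in the same window, the nominal visit is used. SAP 8.7.1 and 8.7.2.2 also define the final visit as Week 12 for completers and the discontinuation visit for everyone else.

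**The concern.** Two of the listed reasons, lack of efficacy and progressive disease, are the efficacy outcome itself. They are judged without a stated threshold, in an open-label trial. If a subject leaves for one of them before Day 70, whether a Week 12 score is missing depends on how the subject was doing. An observed-data summary then describes those who stayed.

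Efficacy is one of the stated objectives (Protocol 3), and SAP 8.7.1 calls PASI change the primary clinical efficacy endpoint. With about ten subjects and no replacement, each lost failure moves a response rate by several percentage points.

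Exit also ends the scheduled vital signs, laboratory tests and ECGs, in a trial that describes itself as primarily about safety and tolerability. In addition, 13.2 lists AEs as a reason to leave the trial, while 14.3 directs continued follow-up for certain AEs. 13.2 does not say how the two fit together.

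**Working it through.** **Inputs**
- N = 10, from Protocol 17.1. The same section says "Sample size calculations were not performed, as this is primarily a safety and tolerability trial", so there is no calculation to reproduce.
- Visit windows: SAP Table 8.5-1.
- Number of responders (r), number of non-responders who exit before Day 70 (w), and all PASI values: assumed, because the documents give no response or dropout rates.

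**Step 1. What happens to an exit score**
- Visit 4 on Day 29, exit on Day 38: both fall in Days 2-41, so the nominal visit is used and the exit score is not.
- Visit 5 on Day 57, exit on Day 64: both fall in Days 42-69, with the same result.
- Visit 4 on Day 29, exit on Day 45: the exit score becomes the Week 8 record. There is no Week 12 record.
- Exit on Day 70 or later: the exit score is eligible as the Week 12 record.

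So under the window table, an exit before Day 70 leaves no Week 12 record. If instead the final-visit sentence in SAP 8.7.1 and 8.7.2.2 governs the Week 12/EOT row, an attended exit visit fills it, but with an earlier score. The SAP does not say which rule prevails.

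**Step 2. Response rate under the window table**

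Observed rate = r / (10 - w); full-group rate = r / 10.

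| r | all ten | w = 1 | w = 2 | w = 3 | w = 4 |
|---|---|---|---|---|---|
| 2 | 20.0% | 22.2% | 25.0% | 28.6% | 33.3% |
| 3 | 30.0% | 33.3% | 37.5% | 42.9% | 50.0% |
| 5 | 50.0% | 55.6% | 62.5% | 71.4% | 83.3% |

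Under the final-visit reading, with exit visits attended and scored as non-response, r = 3 stays at 3/10 = 30.0%.

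**Step 3. Mean PASI change under the window table**

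Assume Baseline PASI 20 for all, with changes of -60% (3 subjects), -25% (4), 0% (1) and +10% (2). In points these are -12, -5, 0 and +2.
- All ten: (3 × -12 + 4 × -5 + 1 × 0 + 2 × 2) / 10 = -52 / 10 = -5.2.
- Without the two worst: (-36 - 20 + 0) / 8 = -7.0.
- Without the three worst: (-36 - 20) / 7 = -8.0.

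**Step 4. Direction**

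The shift is favourable because Steps 2 and 3 remove non-responders. If instead one of 3 responders leaves early, for example for an AE or a deviation, the observed rate is 2/9 = 22.2%, below 30%.

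**Step 5. Safety data after exit**

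Protocol 14.2 collects AEs up to the final trial visit. After exit, what remains is follow-up of test-article-related AEs where possible (13.2), follow-up of AEs still present at the end of participation, as appropriate (14.2), and reporting of SAEs within 30 days of stopping drug if the investigator learns of them (14.4). The scheduled assessments at Days 29, 57 and 85 that feed the safety endpoints are no longer made.

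**The case against.** A reader might infer that 13.2 removes treatment failures, that they are never measured, that sites are told not to collect their data, and that the bias always favours the drug. The documents do not support any of these.
- The wording permits withdrawal and does not direct it. The list also contains death and loss to follow-up, so it partly serves as a set of disposition categories.
- An exit visit with the required assessments is requested whatever the reason.
- An exit on Day 70 or later can supply the Week 12 record, and the final-visit sentence may bring earlier exit scores into Week 12/EOT.
- Exits for AEs, non-compliance or deviation can remove responders.

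It is also fair to say that 14.3 is specific and directive while 13.2 is general, so the two can be read together. Some AE and SAE follow-up continues after exit. The analysis is descriptive, and withdrawal reasons are tabulated (SAP 8.5). The exact 95% interval for 3/10, 6.7% to 65.2%, is much wider than a shift of 3 to 13 points.

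These points limit the concern without removing it. An exit visit before Day 70 is not a Week 12 measurement on any reading of the SAP. A disposition table shows that subjects left, but does not supply their later scores. The wide interval expresses sampling error. It does not correct a shift caused by who remains.

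**Conclusion.** The concern holds in a limited form. Protocol 13.2 allows, without requiring, exit from the trial for reasons that include the efficacy outcome, and provides only a best-effort exit visit. A subject who leaves before Day 70 has no true Week 12 measurement. Under the SAP window table that subject also leaves the Week 12 denominator, and an exit score that shares a window with a nominal visit is not used.

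When the subjects who leave are non-responders, Week 12 PASI, PASI-50/75 and IGA look better than in the full group. With 3 responders of 10, 30% becomes 33%, 38% or 43% for 1, 2 or 3 early exits. In the PASI example the mean change moves from -5.2 to -7.0 or -8.0 for 2 or 3 early exits. These sizes rest on assumed response and dropout numbers, on exit before Day 70, on the window-table reading, and on non-responders being the ones who leave. Other exits may push the result either way.

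Scheduled safety assessments end at exit as well. No hypothesis test or stated power is affected: the harm is to the descriptive efficacy estimates and to safety follow-up. The change is worth making because it is cheap, but it is not a critical defect.

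**What to change.** **Protocol**
- In 13.2, separate stopping test article from leaving the trial, consistent with 14.3. Ask consenting subjects who stop test article for lack of efficacy, progressive disease, non-compliance, deviation or AEs to continue the scheduled assessments through Visit 7.
- Leave pregnancy under 14.6. Leave the decision to stop drug, and withdrawal for a subject's safety, with the investigator.
- Reconcile the AE reason in 13.2 with 14.3.
- Record the last-dose date and any new psoriasis therapy.

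**SAP**
- Flag scores taken after the last dose as off drug, and state whether they enter the Week 12/EOT row. Table 8.5-1 is titled as on-treatment, so this cannot be left implicit.
- State whether the window table or the final-visit sentence governs Week 12/EOT.
- Also report PASI-50 and PASI-75 with all Safety-population subjects in the denominator, counting those without a Week 12 score as non-responders.

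**Cost.** A protocol amendment with IRB approval (Protocol 18.4) and a short SAP change. The visits are already scheduled. Some scores will be off drug and must be shown as such, and some subjects will decline to continue.

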### 13.3 Trial Termination

The trial may be terminated by the investigator or the Sponsor. If, in the opinion of the investigator, clinical observations made during the trial suggest that it may be unwise to continue, he or she may stop the trial. A trial termination by the investigator will be reported to the Sponsor.

In addition, a written statement fully documenting the reasons for trial termination will be submitted to the Sponsor by the investigator within 5 working days.

In the event that the Sponsor chooses to discontinue or terminate the trial, appropriate notification will be given to the investigator.

## 14. ADVERSE EVENT REPORTING

### 14.1 Adverse Event Definitions

An **adverse event** is any untoward medical occurrence associated with the use of a drug in humans, whether or not considered drug related.

An AE (also referred to as an adverse experience) can be any unfavorable and unintended sign (e.g., an abnormal laboratory finding), symptom, or disease temporally associated with the use of a drug, without any judgment about causality. An AE can arise from any use of the drug (e.g., off-label use, use in combination with any drug) and from any route of administration, formulation, or dose, including an overdose.

A **suspected adverse reaction** is any AE for which there is a reasonable possibility that the drug caused the event. “Reasonable possibility” means there is evidence to suggest a causal relationship between the drug and the AE.

An **adverse reaction** is any AE caused by a drug. Adverse reactions are a subset of all suspected adverse reactions for which there is reason to conclude that the drug caused the event. A suspected adverse reaction implies a lesser degree of certainty about causality than adverse reaction, which means any AE caused by a drug. For the purposes of prescription drug labeling, the term adverse reaction means an undesirable effect, reasonably associated with the use of a drug that may occur as part of its pharmacological action or may be unpredictable in its occurrence.

An AE or suspected adverse reaction is considered “unexpected” if it is not listed in the Investigator’s Brochure (IB) or is not listed at the specificity or severity that has been observed; or, if an IB is not required or available, the event is considered “unexpected” if it is not consistent with the risk information described in the general investigational plan or elsewhere in the current application. For example, under this definition, hepatic necrosis would be unexpected (by virtue of greater severity) if the IB referred only to elevated hepatic enzymes or hepatitis. Similarly, cerebral thromboembolism and cerebral vasculitis would be unexpected (by virtue of greater specificity) if the IB listed only cerebral vascular accidents. “Unexpected,” as used in this definition, also refers to AEs or suspected adverse reactions that are mentioned in the IB as occurring with a class of drugs or as anticipated from the pharmacological properties of the drug, but are not specifically mentioned as occurring with the particular drug under investigation.

Timely and complete reporting of all AEs assists the Sponsor and/or their designee (e.g., Therapeutics, Inc. [TI]) in identifying any untoward medical occurrence, thereby allowing:

- 1) protection of the safety of trial subjects;
- 2) a greater understanding of the overall safety profile of the test article;
- 3) recognition of dose-related test article toxicity;
- 4) appropriate modification of trial protocols;
- 5) improvements in trial design or procedures; and
- 6) adherence to worldwide regulatory requirements.

#### **14.2 Adverse Event Details**

[figure not shown]
AEs may be either spontaneously reported or elicited during questioning and examination of a subject. All AEs must be recorded on the AE eCRF. If known, the investigator should report the diagnosis of the underlying illness or disorder, rather than its individual symptoms. Subjects experiencing AEs that cause interruption or discontinuation of test article or those experiencing AEs that are present at the end of their participation in the trial should receive follow-up as appropriate. AEs should be followed to resolution or stabilization (if possible) and, if they become serious, reported as serious adverse events (SAEs, see Section 14.4). If possible, the outcome of any AEs that caused permanent discontinuation or that were present at the end of the trial, especially those considered by the investigator to be related to the test article, should be reported.

Information on the medical condition of subjects should begin following the subject’s written informed consent to participate in the trial and a medical history should be taken at screening. During any wash out and screening periods, any changes in the health of subjects should be recorded as changes in medical history unless an event occurred as a result of a trial-related procedure and is unanticipated; in such cases, the event should be recorded as an AE and reported to the Institutional Review Board (IRB) as an “unanticipated problem” in accordance with local procedures. Other changes in subject health information becomes AE data when the subject begins dosing with the test article; therefore AE data should be

collected from the date of the first dose of test article until the date of the final trial visit. These data are considered treatment-emergent AEs.

In clinical trials in healthy humans exposed to ADX-629, AEs deemed unrelated to test article included sinus congestion, headache, nasal congestion, upper respiratory tract infection, and rhinitis. One AE deemed possibly related to test article included syncope of moderate intensity.

The investigator will instruct the subject to report any AEs that may occur during the trial. At each visit, the investigator should ask the subject, in non-directive fashion, about any change in the subject's overall health status since the previous visit.

The investigator must determine the relationship of the AE to the test article according to the following categories:

**Definitely Related:** An event that follows a reasonable temporal sequence from administration of the test article; that follows a known or expected response pattern to the test article; and that is confirmed by improvement on stopping or reducing the dosage, and reappearance of the event on repeated exposure (re-challenge).

**Probably Related:** An event that follows a reasonable temporal sequence from administration of the test article; that follows a known or expected response pattern to the test article; and that is confirmed by improvement on stopping or reducing the dosage of the test article; and that is unlikely to have been caused by concurrent/underlying illness or other drugs, procedures, or other causes.

**Possibly Related:** An event that follows a reasonable temporal sequence from administration of the test article; that follows a known or expected response pattern

to the test article; but may have been caused by concurrent/underlying illness, other drug, procedure, or other causes.

**Unlikely Related:** An event that does not follow a reasonable temporal sequence from administration of the test article; that does not follow a known or expected response pattern to the test article, or most likely was caused by concurrent/underlying illness, other drug, procedure, or other causes, because of their known effects.

**Not Related:** An event almost certainly caused by concurrent/underlying illness, other drug, procedure, or other causes.

The investigator should categorize the outcome of the AE according to the following categories:

**Fatal:** Termination of life as a result of an AE.

**Not Recovered/Not Resolved:** AE has not improved or the subject has not recuperated.

**Recovered/Resolved:** AE has improved or the subject has recuperated.

**Recovered/Resolved with Sequelae:** Subject recuperated but retained the pathological conditions resulting from the prior disease or injury.

**Recovering/Resolving:** AE is improving or the subject is recuperating.

**Unknown:** Not known, not observed, not recorded or subject refused.

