## 1. BACKGROUND

Reactive aldehyde species (RASP) such as 4-hydroxynonenal and malondialdehyde (MDA) are toxic mediators of the mammalian immune system and are implicated in numerous disease states. The Sponsor has developed ADX-629, a proprietary new chemical entity for the treatment of immune-mediated diseases, including psoriasis, asthma, inflammatory bowel disease, alcoholic and non-alcoholic hepatitis, acute respiratory distress syndrome, and other diseases that are thought to be caused or exacerbated by elevated concentrations of RASP.

MDA is elevated in the plasma of patients with psoriasis [1], reaching levels of approximately 4 $\mu$ M, roughly twice that of healthy subjects. A recent review [2] highlights the correlation of MDA levels with psoriasis area severity index (PASI), as well as increased levels of MDA in patients with genetic polymorphisms that increase the risk of psoriasis.

[REDACTED]

[REDACTED]

[REDACTED]

In addition to nonclinical safety studies, Phase 1 safety testing has been conducted in 85 healthy human volunteers in a single ascending dose (SAD) and a multiple ascending dose (MAD) clinical trial. In the SAD portion of the clinical trial, 41 subjects received drug and 13 received placebo across all cohorts. In the MAD portion of the clinical trial, 23 subjects received drug and 8 received placebo across all cohorts for 10 days. Overall, ADX-629 was found to be safe and tolerable at the doses explored, including the maximum single dose of 1200 mg and the maximum multiple dose of 600 mg BID for 10 days. The adverse event profile of ADX-629 was favorable compared to placebo. A total of 6 (9.4%) subjects receiving ADX-629 had treatment emergent adverse events compared to 4 (19.1%) subjects who received placebo. None of the subjects had an interruption or discontinuation of the trial drug.

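### Every related category in Protocol 14.2 demands an already recognised or anticipated drug response, so a new kind of reaction with plausible timing cannot be coded as related

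*Protocol*

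**What the plan says.** Protocol Section 14.2 gives the investigator five causality categories. Definitely, Probably and Possibly Related all begin with "An event that follows a reasonable temporal sequence from administration of the test article; that follows a known or expected response pattern". They then differ on improvement after stopping or reducing the dose, re-challenge and other causes. Unlikely Related starts with implausible timing and continues "that does not follow a known or expected response pattern to the test article, or most likely was caused by concurrent/underlying illness". Not Related is kept for events almost certainly due to something else.

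Section 14.1 sets a different standard. A suspected adverse reaction is "any AE for which there is a reasonable possibility that the drug caused the event", and no prior pattern is required. The same section defines unexpected suspected reactions, chiefly those not listed in the Investigator's Brochure.

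Section 13.2 points to Section 14.2 as the definition of a test article related AE. In Section 14.3 all four enrolment-review conditions are worded in terms of attribution, for example "SAE considered related to trial drug". So is at least the cardiac and blood limb of the first subject stopping rule. SAP Section 8.8.3 tabulates events by the same five categories and gives no grouping into related and unrelated.

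**The concern.** Protocol Section 17.1 calls this primarily a safety and tolerability trial, and causality is part of safety endpoint 1 (Section 17.2.1). A drug early in development is studied partly to find reactions that nobody has yet described. A causality scale that demands a prior pattern before an event can be called even Possibly Related works against that aim. It would pull the causality table away from the related categories for exactly the events of most interest. If the same coding is used to decide whether an event counts as related in Section 14.3, it could also affect when those rules are considered met.

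**Working it through.** **Step 1: prior human experience.** Protocol Section 1 reports that in the single-dose part "41 subjects received drug and 13 received placebo across all cohorts", and in the multiple-dose part "23 subjects received drug and 8 received placebo across all cohorts for 10 days".
- On drug: 41 + 23 = 64. All subjects: 41 + 13 + 23 + 8 = 85, as stated.
- Treatment-emergent events on drug: 6/64 = 9.375%, which reproduces the stated 9.4%.
- On possible drug effects in humans, Section 14.2 says: "One AE deemed possibly related to test article included syncope of moderate intensity".

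**Step 2: how much could be unseen.** If a reaction was seen in 0 of n subjects, the one-sided 95% upper bound on its rate is 1 − 0.05^(1/n).
- n = 64: 1 − 0.05^(1/64) = 4.6%.
- n = 23 (multiple dosing, 10 days): 1 − 0.05^(1/23) = 12.2%.

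This trial doses patients for 12 weeks, so neither bound covers reactions that need longer exposure or the disease.

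**Step 3: apply the definitions to an event with plausible timing and no known or anticipated pattern.** The Unlikely Related definition has the form A; B, or C, where A is implausible timing, B is no pattern and C is another cause most likely. It can be read with A, B and C as alternatives, or with A and B required together.

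| Other cause | Definitely, Probably or Possibly | A, B, C as alternatives | A and B required together |
|---|---|---|---|
| Unlikely | not met | Unlikely | no category |
| May have contributed | not met | Unlikely | no category |
| Most likely | not met | Unlikely | Unlikely |

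If another cause is almost certain, Not Related applies on either reading. Improvement on stopping, or recurrence on re-challenge, does not change the second column, because the pattern condition comes first in all three related definitions.

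**Step 4: compare with Section 14.1.** The event in the first two rows can meet the reasonable-possibility test. It can also be an unexpected suspected reaction, a class that Section 14.1 defines. Section 14.2 has no related category in which to record it.

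**Step 5: illustration of what coding can do at N = 10.** The documents give neither a true reaction rate p nor the share s of such events that would be coded related. Both are assumptions here. With q = p × s, the chance that two or more of 10 subjects count is 1 − (1 − q)^10 − 10q(1 − q)^9.

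| p | s = 1 | s = 0.5 | s = 0 |
|---|---|---|---|
| 10% | 26% | 9% | 0% |
| 20% | 62% | 26% | 0% |
| 30% | 85% | 46% | 0% |

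The table shows only how sensitive a two-subject count is to coding. It does not predict how Section 14.3 would operate, because that section does not name the Section 14.2 scale.

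**The case against.** Four stronger readings are tempting, and the documents do not support them.

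- **New reactions default to Unlikely Related.** That is one parse. In the three definitions above it, semicolons join cumulative conditions. Read the same way here, the event falls in no category and is left to judgment. This objection stands, but on neither parse is the event related.
- **The recognised pattern is close to empty.** The condition also admits anticipated effects, which may come from pharmacology, nonclinical work or the Investigator's Brochure. The Brochure is not available here, and parts of the Background are redacted. The objection stands as a limit. Section 14.1 itself treats effects anticipated only from pharmacology as unexpected, but Section 14.2 does not say whether it adopts that sense.
- **The Section 14.3 rules would fail to operate.** The anaphylaxis, renal, haemodialysis and hepatic stops do not use attribution. Section 14.4 requires every SAE to be reported immediately, with an assessment of reasonable possibility, so the Section 14.1 standard already reaches serious events. The Medical Monitor reviews safety data on an ongoing basis and makes the enrolment decision. Whether the relatedness phrase in the first subject rule also governs its Grade 3 limb is ambiguous. What remains exposed is mainly non-serious events.
- **One recoded event moves the related-AE rate by 10 points.** One subject in 10 moves any incidence by that much. The SAP plans no collapsed related rate; it tabulates all five categories and lists every event. Overall AE incidence is unaffected.

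**Conclusion.** The point holds as a conflict of definitions. Followed literally, Section 14.2 gives no related category to an event with plausible timing and no recognised or anticipated pattern, whichever way Unlikely Related is parsed, while Section 14.1 accepts such events as suspected reactions. The cross-reference in Section 13.2 makes Section 14.2 the operative definition of relatedness for that purpose.

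The definite effect is on the causality table of SAP Section 8.8.3. An effect on the attribution wording of Section 14.3 is possible, mainly for non-serious events, and the documents do not establish it. No planned numerical result can be shown to change by a given amount. The size rests on how thin prior experience is: 64 subjects on drug, with bounds of 4.6% and 12.2% for a reaction not yet seen. It also rests on investigators applying the definitions as written; those who use judgment, or read anticipated effects broadly, would narrow the gap without closing it. The change is worth making because it is cheap and concerns a main safety output.

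**What to change.** Reconcile Section 14.2 with Section 14.1.
- Reword Definitely, Probably and Possibly Related so that a recognised or anticipated pattern supports the category but is not necessary for any of the three. Changing Possibly alone is not enough. Its last clause refers to another possible cause, so a new reaction that improves on stopping and has no other explanation would still fit nowhere.
- Reword Unlikely Related so that lack of a pattern is not by itself a ground for it, and so that the definition has only one parse.
- In SAP Section 8.8.3, state how the five categories are grouped if a related/unrelated summary is made.
- Reconcile Sections 14.1, 14.2 and 14.3 so that Section 14.3 says which causality assessment it relies on and which limbs of the first subject rule the relatedness phrase governs. The sponsor decides the cut.

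The cost is wording in the protocol, the eCRF guidelines and the SAP. The count of related events would probably rise somewhat, which could lead to more safety reviews.
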